## Outcomes of interest

### Primary

The primary effectiveness outcome will be time to psychiatric hospitalization.

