### Secondary

We will also investigate time to index treatment discontinuation, time to introduction of another psychotropic medication, psychiatric emergency department visits, all-cause hospitalization, and death.

We will investigate adverse effects of medications including incidence of major cardiovascular events and diabetes mellitus.

Outcomes	
Death	Date of death will be defined by the Social Security Death Master File.
Psychiatric Hospitalization	Hospital claims will define inpatient admissions with a first listed mental disorder diagnosis (ICD-9:290-310). High levels of agreement between diagnoses in inpatient medical records and inpatient claims have been reported for several mental disorder groups, including schizophrenia (100.0%), major mood disorders (98.7%), alcohol dependence (97.8%), and drug dependence (96.4%). 
Psychiatric ED Visits	Emergency department claims are a reliable source of diagnostic information in relation to medical records and a valid source of illness severity information.  Emergency department visits in which the first listed diagnosis is a mental disorder (ICD-9-CM: 290-319) will be defined as emergency department mental health visits.
Self-Injurious Behavior	Deliberate self-harm will be defined by an E-code of E950-E958, excluding late effects of deliberate self-harm (E959), on any inpatient, emergency department, or outpatient claim. High positive predictive values have been reported. 
Diabetes Mellitus	One or more claims with a physician diagnosis of diabetes will define diabetes mellitus. Using self-reported diabetes status as the criterion standard, $\geq 1$ physician claim with any diagnosis of diabetes or a diabetes complication (ICD-9 codes: 295.00-2950.93, 357.2, 362.0-362.02, 366.41) has acceptable sensitivity (68.5%) and specificity (96.9%), and (kappa=0.76).  Sensitivity of 90% and specificity of 93% with self-reported diabetes. 
Cardiovascular Events:	Acute myocardial infarction (AMI) (ICD-9-CM: 410) or stroke (430-438, except 435) will be defined by diagnostic codes on inpatient claims of $\geq 3$ days in duration.  With this AMI definition 75% met criteria for definite or probable AMI on independent review of cardiac biomarkers, electrocardiograms, presenting symptoms, and medical history, and an additional 12% had a suspected AMI. 

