## Approach to confounding

Physicians make treatment choices in light of available clinical information and as a result there is a risk of confounding by clinical indication for the treatments under study. Our design minimizes confounding by indication by focusing on diagnostic subgroups. To further reduce confounding, we will control for a broad range of potentially relevant factors from claims histories. These factors will be identified in the 365-day period before drug initiation and used to calculate propensity scores. In addition we will conduct sensitivity analyses to estimate the extent of unmeasured confounding necessary to fully explain our observed findings and we will conduct instrumental variable analyses if a suitable instrument is identified.

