### *Propensity score estimation and application*

Propensity score methods involve two steps: estimation of the propensity scores and application of the propensity score. Estimation of the propensity scores involves decisions about which covariates to include in the prediction model of the propensity scores and what form the model should take. We will use expert opinion to select the variables to include in the propensity score. To estimate the propensity scores we will first use logistic regression including all baseline predictors occurring prior to treatment assignment. In addition, we will augment our analysis with another non-parametric method for building the propensity score model such as a generalized boosting algorithm implemented with regression trees. We will assess the sensitivity of our results to the choice of the propensity score model.

For the application of the propensity scores, we will use weighting by the odds to estimate the average treatment effect on the treated sample and weighting by the inverse probability of treatment weights to estimate the average treatment effect in the population.

We will examine the covariate balance using standardized differences in covariate means across the treatment groups after weighting, and address any significant imbalances.

**AIM 2 Heterogeneity of Treatment Effects:** Within the five subgroups, explore whether the comparative effectiveness and safety of alternative treatment strategies varies according to patient age and presence of a substance use disorder.

We will use similar Cox model techniques for the HTE analyses. First we will assess interaction of age and substance use variables with treatment. If such interactions are found, we will then perform analyses examining alternative treatment strategies stratified by age group or substance use.

The rationale for investigating patient age as a moderator of antipsychotic treatment effects follows from evidence that individuals early in the course of psychosis may respond differently to medications than people with more chronic illness. The rationale for investigating comorbid diagnosis of a substance use disorder as a moderator of treatment effects follows from evidence that people diagnosed with schizophrenia and comorbid substance use disorders respond more poorly to antipsychotic medications than those without comorbid substance use disorders.

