### Sensitivity Analyses

We will conduct sensitivity analyses to confirm findings from the primary analyses and to examine their generalizability. In addition to the primary 360-day intention-to-treat analyses we will conduct 180-day intention-to-treat analyses and as-treated analyses. Another sensitivity analysis will examine subgroups of people with depression, anxiety, or mania diagnoses that are listed by more than one provider.

**Quantitative Sensitivity Analyses for Unmeasured Confounders.** Because the observed relative risk is a closed-form function of the balance of confounders among exposure groups, the strength of the confounder, and the prevalence of the confounder, it is possible to estimate the extent of unmeasured and thus unadjusted confounding necessary to fully explain the observed findings, i.e., would move the observed relative risk to statistical insignificance (the null).

To quantify how strong unmeasured confounding would have to be to explain the observed effect sizes among our comparison groups, we will use the array approach to understand how the strength of unmeasured confounders with known associations with our outcomes, such as BMI and risk of diabetes, and the confounder imbalance among study groups might affect the observed relative risk.

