#### AP treatment Initiation year

2002

2003

2004

2005

2006

2007

2008

2009

Diagnostic History, past year	ICD-9-CM Codes*
Depression	293.83, 296.2x, 296.3x, 296.9x, 298.0x, 300.4x, 311.xx
Anxiety	293.84, 300.0x, 300.2x, 300.3x, 308.3x, 309.21, 309.81, 313.0x, 313.2x, 313.89
Bipolar	296.xx (not 296.2x or 296.3x or 296.9x)
Substance use disorder	291.xx, 292.xx, 303.xx, 304.xx
Moderate/severe mental retardation	318.xx
HIV	042, 043, 044, 079.53, V08
Neoplasms	140.xx-239.xx (Exclude people with malignant neoplasms 140.xx-205.xx)
Diabetes	250.xx
Obesity	270.xx
Hyperlipidemia	272.0x-272.4x, 272.7x, 272.9x
White blood cell diseases	288.xx, 289.xx (exclude neutrophil d/o 288.00-288.04, 288.09, 288.1x)
Anemia	280.xx-285.xx
Drug-related dyskinesia	333.85
Hypertension	401.xx-405.xx
Ischemic heart disease	410.xx-414.xx
Pulmonary circulation diseases	415.xx-417.xx
Cardiac dysrhythmias	427.xx
Heart failure	428.xx
Cerebrovascular disease	430.xx-438.xx
Acute bronchitis and bronchiolitis	466.xx
Chronic bronchitis	491.xx
Pneumonia	480.xx-486.xx
Emphysema	492.xx
Asthma	493.xx
Appendicitis	540.xx-543.xx
Noninfectious enteritis and colitis	555.xx-558.xx
Diverticula of intestine	562.xx
Intestinal obstruction	560.xx
Chronic liver disease and cirrhosis	571.xx
Acute & chronic pancreatitis	577.0x, 577.1x
Cholelithiasis	574.xx
Acute kidney failure	584.xx
Chronic kidney failure	585.xx

Kidney infections	590.xx
Cellulitis and abscess	681.xx–682.xx
Osteoarthritis and allied disorders	715.xx
Intervertebral disc disorder	722.xx
Fractures, all sites	800.xx–829.xx
Fracture of neck of femur	820.xx
Poisoning by psychotropic medication	969.xx
Poisonings	960.xx–989.xx
Suicide and self-inflicted injury	E950-959
Intracranial injury	815.xx-854.xx
Severe cardiovascular diseases	401.0x-404.9x, 410.xx-416.xx, 425.xx-437.xx, 440.xx-447.xx
Schizophreniform	295.4x
Schizoaffective	295.7x

---

\* x indicates inclusion of any 5th digit if available for a diagnosis code.

xx indicates inclusion of any 4th and 5th digits if available for a diagnosis code.

Medication history, past year	Drug class
Psychotropic medication	
Antidepressants	SSRI/SNRI/mirtazapine, TCA and heterocyclic compounds, MAOI, trazodone-related antidepressants, bupropion
Mood Stabilizer	lithium, primary anticonvulsant, secondary anticonvulsant
ADHD medication	psychostimulants, alpha-agonists
Anxiolytic/hypnotics	benzodiazepines, GABA agonists, other newer or older anxiolytic/hypnotic

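### The ICD-9-CM code printed for the obesity covariate does not match its label, so a score programmed as printed would contain no direct obesity diagnosis

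*Combined protocol and SAP*

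**What the plan says.** Appendix 2 (Variables included in the Propensity Score) has a table of past-year diagnoses with a column of ICD-9-CM codes. The row at issue is "Obesity 270.xx". The table's footnote explains the suffix: "xx indicates inclusion of any 4th and 5th digits if available for a diagnosis code".

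The listed covariates are operative. Approach to confounding says: "These factors will be identified in the 365-day period before drug initiation and used to calculate propensity scores". Propensity score estimation and application adds: "we will first use logistic regression including all baseline predictors occurring prior to treatment assignment". The same section then checks balance after weighting by standardized differences in covariate means.

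The secondary outcomes include adverse effects, namely "incidence of major cardiovascular events and diabetes mellitus". For the primary outcome the plan says: "The primary effectiveness outcome will be time to psychiatric hospitalization". Under Sensitivity Analyses, the array approach is assigned to "unmeasured confounders with known associations with our outcomes, such as BMI and risk of diabetes".

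**The concern.** By listing obesity, the plan judged it worth adjusting for. The code beside the label appears to denote something else. A covariate list of this kind is a programming specification, and an analyst who follows it literally builds a variable that flags rare metabolic disorders and calls it obesity.

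At stake are the comparisons on incident diabetes and major cardiovascular events. Body weight is plausibly related to both, and prescribers may plausibly weigh it when choosing among a second antipsychotic, a mood stabilizer, an antidepressant and a benzodiazepine. Claims capture obesity incompletely, but the recorded part could be adjusted for with data already in hand. As printed, that part is not used.

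**Working it through.** The plan states no figure that depends on this code, so there is nothing to reproduce. The check is textual, followed by an illustration of scale.

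**1. What the printed row can capture.** By the footnote, 270.xx reaches only codes that begin with 270. It cannot reach 278.0x.

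**2. Whether another row fills the gap.** Appendix 2 has no other obesity or BMI diagnosis row, and 278 appears nowhere in the documents.

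**3. What the score still contains.** The related diagnoses are diabetes (250.xx), hyperlipidemia (272.0x-272.4x, 272.7x, 272.9x), hypertension (401.xx-405.xx) and ischemic heart disease (410.xx-414.xx). The medication history includes lipid-lowering drugs, anorexiants, antihypertensives and diabetic medication. These are partial proxies for weight. The plan speaks of the incidence of diabetes but states no exclusion of prevalent cases. If people with diabetes at baseline are left out of that analysis, the diabetes diagnosis and diabetic-medication covariates would hardly vary and could not help there.

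**4. Whether the balance check would catch it.** For a binary covariate the standardized difference is (p1 − p0) / √{[p1(1 − p1) + p0(1 − p0)] / 2}. With a correct code and the prevalences assumed in step 5, the values before weighting would be:

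- 15% vs 10%: 0.05 / √[(0.1275 + 0.09) / 2] = 0.05 / 0.330 = 0.15
- 20% vs 10%: 0.10 / √[(0.16 + 0.09) / 2] = 0.10 / 0.354 = 0.28

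A variable near zero in every arm would show no meaningful difference, so a row labelled obesity would look balanced whatever the true imbalance.

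**5. Illustration of scale.** The documents give no obesity prevalence, arm imbalance or risk ratio, so all inputs here are assumptions. The usual bias factor for one unadjusted binary confounder, the kind of closed-form relation on which the plan's array approach rests, is

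bias = [1 + p1(RR − 1)] / [1 + p0(RR − 1)]

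Here p1 and p0 are the prevalences of recorded obesity in the two arms, and RR is the effect of obesity on the outcome.

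| p1 vs p0 | RR 1.5 | RR 2 | RR 3 | RR 4 |
|---|---|---|---|---|
| 15% vs 10% | 1.075/1.05 = 1.024 | 1.15/1.10 = 1.045 | 1.30/1.20 = 1.083 | 1.45/1.30 = 1.115 |
| 20% vs 10% | 1.10/1.05 = 1.048 | 1.20/1.10 = 1.091 | 1.40/1.20 = 1.167 | 1.60/1.30 = 1.231 |

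For RR 2 to 4 the spurious risk ratio runs from about 1.05 to 1.23. These values treat obesity as independent of every other covariate. After weighting on the proxies in step 3, the remaining imbalance and association should be smaller, and the bias with them. The bias is substantial only if obesity is both clearly imbalanced and strongly related to the outcome.

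**The case against.** Four objections carry weight.

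- **The code meanings are not in the documents.** Nothing internal contradicts 270.xx. This stands as a reason to confirm first. It does not remove the point, because the plan adopts a public code set and one lookup settles the matter.
- **The printed code may not be the programmed one.** A one-character typing or PDF-reading error cannot be excluded. The code lists have other visible slips: the diabetes outcome is printed as 295.00-2950.93 while the diabetes covariate is 250.xx, and intracranial injury (815.xx-854.xx) overlaps fractures at all sites (800.xx-829.xx). So the consequence is conditional. Equally, these slips suggest that the lists were not proofread, which is a reason to check the program.
- **The plan already treats BMI as unmeasured.** It gives BMI an array analysis, with diabetes as the example, and a corrected diagnosis code would still not supply BMI. That is true. But an array shows how strong a confounder would have to be; it does not adjust for the part that claims record.
- **Near-zero obesity would look implausible in a baseline table.** An alert analyst might well notice. The planned standardized-difference check would not flag it by itself.

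A reader might infer that the diabetes and cardiovascular comparisons go wholly unadjusted for weight-related risk, or that the study's main result is compromised. The documents support neither. Several proxies are in the score, and the primary outcome is psychiatric hospitalization, for which no effect of this code has been shown.

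**Conclusion.** The covariate definition is wrong as written, given the standard meaning of the ICD-9-CM categories. If it was programmed as printed, a covariate the plan meant to include is missing from the propensity score, and only partial proxies stand in for it.

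The consequence falls mainly on the secondary safety outcomes. Its size and direction cannot be derived from the documents; the 1.05 to 1.23 range is an illustration under assumed inputs and, because it ignores proxy control, probably too large. No sample-size or power figure changes. The point should be fixed. It does not rank as a must-fix, because it is conditional on the program, concerns secondary outcomes, and is partly covered by the proxies and the planned BMI sensitivity analysis.

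**What to change.** 1. Check the obesity row against ICD-9-CM and against the code list in the analysis program.
2. Correct Appendix 2 to 278.0x.
3. If 270.xx was run, re-estimate the propensity scores and repeat the weighted analyses.
4. Report recorded obesity by treatment arm, before and after weighting, within each clinical subgroup.
5. Keep the BMI arrays for the part of body weight that claims do not record.

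The cost is one code in the appendix and, at most, a re-run of the scores and the models that use them. No new data are needed.

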Current practice patterns vary widely. In our preliminary analyses, we found wide variation in prescribing of different classes of psychotropic medications to patients with schizophrenia in the year prior to initiation of a new antipsychotic medication, providing additional evidence regarding uncertainty of these treatment strategies. Across states, rates varied by 2 to 3 fold. Specifically, the initiation of benzodiazepines varied from 9.2% (Kentucky) to 29.7% (Vermont); antidepressants from 19.8% (Vermont) to 48.3% (Oklahoma); and mood stabilizers from 6.6% (North Dakota) to 18.9% (Texas). Such variation underscores deficiencies in widely accepted clinical evidence concerning these important treatment decisions.

There is no professional consensus on treatments for important subgroups with schizophrenia. Schizophrenia treatment guidelines and algorithms have concluded that there is little evidence to guide selection of pharmacologic strategies for schizophrenia beyond the initial recommendation for antipsychotic monotherapy and then for clozapine for people with treatment-resistant illness.

Although there is limited information on the clinical comparisons we propose to study, recent evidence from a Finnish observational study of psychotropic polypharmacy in schizophrenia, which used methods that are similar to those that we propose, found substantial effect sizes. In that study, for example, there was a significant increase in mortality associated with adjunctive benzodiazepine use compared to antipsychotic monotherapy and adjunctive antidepressant use was associated with markedly reduced risk of suicide.

Despite the widespread use of various combinations of classes of psychotropic medicines in schizophrenia, their comparative safety and effectiveness have not been established. By determining which options are most effective in achieving desired outcomes in specific clinical situations, this project will promote personalized, evidence-based medicine and has the potential to reduce wasteful or harmful medication management approaches. By helping doctors and patients find effective treatments earlier than by simple trial and error, this project has the potential to reduce the potential harms and inconvenience of failed medication trials, adverse effects, and unnecessary hospitalizations.

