### Comparators

Pharmacological treatment options for patients with schizophrenia who are nonresponsive to antipsychotic monotherapy will include (1) initiation of a second antipsychotic, (2) initiation of an antidepressant, (3) initiation of a mood stabilizer and (4) initiation of a benzodiazepine.

Within each clinical subgroup, treatment options may be refined by exclusions at the drug class or individual agent level. For example, antidepressants are generally not considered treatment alternatives in patients presenting with mania, but could reasonably be considered for patients in the remaining four schizophrenia subgroups: depression, anxiety, schizoaffective disorder, and uncomplicated schizophrenia. Unless it is not considered a reasonable treatment option for a specific subgroup, initiation of a new antipsychotic will serve as the reference category because it is a frequently recommended approach to improving treatment response and is a common treatment strategy across all of the clinical subgroups under study. A survey on the prescribing behaviors of clinicians who prescribe psychotropic medications for individuals with schizophrenia will inform these choices.

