Other psychiatric medication	modafinil, oxybate, phendimetrazine, benzphetamine
OB/GYN medication	oral contraceptives, other contraception, medroxyprogesterone
Metabolic and related medication	lipid-lowering drugs, hypothyroid treatment, antithyroid agents, anorexiant
Cardiovascular medication	thiazide diuretic, ACE inhibitor/ARBs, other anti-hypertensives, other cardiovascular drugs
Respiratory/allergy medication	non-sedating antihistamines, other antihistamines, Corticosteroids, other Asthma medications, Smoking cessation
Gastrointestinal medication	histamine 2 receptor antagonists, proton-pump inhibitors, other prescription dyspepsia, Antacids, anti H pylori, phenothiazine antiemetics, Ulcerative colitis treatment
Neurologic/musculoskeletal medication	migraine treatment/prevention, NSAID, includes coxibs, narcotic analgesic, Non-narcotic analgesic (acetaminophen), Cyclobenzaprine, other skeletal muscle relaxants, other rheumatologic
Antibiotics	
Diabetic medication	
Hyperlipidemia medication	
Severe cardiovascular medication	

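### The propensity score lists chronic bronchitis, emphysema and asthma but omits ICD-9-CM 496, so COPD coded only there is balanced only through proxies when death and all-cause hospitalization are compared.

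*Combined protocol and SAP*

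**What the plan says.** Appendix 2, Diagnostic History, lists the past-year diagnoses that enter the propensity score. The lung rows are "Acute bronchitis and bronchiolitis" (466.xx), pneumonia (480.xx-486.xx), "Chronic bronchitis" (491.xx), emphysema (492.xx) and asthma (493.xx). Pulmonary circulation disease (415.xx-417.xx) has its own row. No row is labelled COPD. The footnote on wildcards says that "xx indicates inclusion of any 4th and 5th digits if available for a diagnosis code".

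The medication part of Appendix 2 has a respiratory and allergy group. After two antihistamine classes it lists "Corticosteroids, other Asthma medications, Smoking cessation".

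Under Outcomes of interest, "The primary effectiveness outcome will be time to psychiatric hospitalization". The secondary outcomes include "psychiatric emergency department visits, all-cause hospitalization, and death". The Comparators section names four strategies, the last being "4) initiation of a benzodiazepine". A second antipsychotic is the usual reference.

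The section on propensity score estimation says that covariates are chosen by expert opinion, and that balance after weighting is judged by standardized differences in covariate means.

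**The concern.** The list takes in the chronic airway codes next to 496, and conditions as remote as appendicitis and gallstones, but not the code for chronic airway obstruction without further specification. No reason is given, so the gap looks like an oversight.

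A patient with only 496 claims in the look-back year is treated by the score as free of chronic airway disease. If such patients are unevenly spread across strategies and have a higher risk of death or admission, part of that difference can pass as a drug effect.

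The planned checks need not reveal it. Standardized differences are examined for the covariates in the model, and 496 is not one of them. The health-service covariates in Appendix 2 count psychiatric and psychosocial care, not earlier medical admissions. Tobacco use is named in no diagnosis row, so smoking enters only through cessation drugs.

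**Working it through.** The plan states no figure on this point, so there is none to reproduce. Two checks apply.

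**1. Is 496 covered by any row?** Under the footnote, xx adds fourth and fifth digits to the three-digit code shown, so 491.xx stays within 491. The listed codes and ranges nearest to 496 are 480-486, 491, 492 and 493 below it and 540-543 above it. The heart and vascular ranges, including the composite row for severe cardiovascular disease, end at 447. No row reaches 496. (The meaning of 496 comes from the ICD-9-CM classification. The documents do not mention the code.)

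**2. How large could the residual bias be?** The Sensitivity Analyses section adopts the array approach. Its closed form for a binary confounder is

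bias factor = [1 + P1(RR - 1)] / [1 + P0(RR - 1)]

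where P1 and P0 are the prevalences of 496-only COPD in the two arms and RR is its relative risk for the outcome. None of these is in the documents. Assume P1 of 3-5%, P0 of 5-10% and RR of 2-3, with no control through proxies:

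| P1 | P0 | RR | Calculation | Bias factor |
|---|---|---|---|---|
| 5% | 5% | any | equal prevalences | 1.00 |
| 3% | 5% | 2 | 1.03 / 1.05 | 0.981 |
| 5% | 10% | 2 | 1.05 / 1.10 | 0.955 |
| 3% | 10% | 2 | 1.03 / 1.10 | 0.936 |
| 5% | 10% | 3 | 1.10 / 1.20 | 0.917 |
| 3% | 10% | 3 | 1.06 / 1.20 | 0.883 |

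If the imbalance is reversed, the factors are the reciprocals, up to 1 / 0.883 = 1.13.

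A second set of assumptions starts from all COPD and applies the share coded only as 496. Take the share as 20-80%, prevalence as 5-10% in the reference arm, the ratio between arms as 1.2-2.0, and RR as 1.5-3:

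- Low: share 20%, 6% versus 5%, RR 1.5: (1 + 0.012 x 0.5) / (1 + 0.010 x 0.5) = 1.006 / 1.005 = 1.001.
- Middle: share 60%, 15% versus 10%, RR 2: 1.09 / 1.06 = 1.028.
- High: share 80%, 20% versus 10%, RR 3: (1 + 0.16 x 2) / (1 + 0.08 x 2) = 1.32 / 1.16 = 1.138.

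Both sets run from almost nothing to about 12-14% on the ratio scale. Respiratory drugs and co-recorded codes would shrink these values.

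**The case against.** The strongest reply is that the score already controls for much of this. It contains 491, 492, 493, acute bronchitis, pneumonia, pulmonary circulation disease, heart failure, corticosteroids, asthma drugs, smoking-cessation drugs, antibiotics and age in narrow bands. A patient with 496 who also has a 491-493 claim in the same year is captured. This stands: the gap is confined to patients with 496 alone, and mainly those without respiratory drugs. It does not close the gap, because the drug group mixes COPD with asthma and allergy and misses untreated patients.

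A second reply is precision. Assume 1-2% one-year mortality, which the documents do not give. The largest benzodiazepine contrast in Table 5 (12,248 versus 27,005 episodes) then has about 122 versus 270 deaths, or 245 versus 540. The 95% half-width on the log ratio is 1.96 x sqrt(1/122 + 1/270) = 0.21, or 1.96 x sqrt(1/245 + 1/540) = 0.15. The largest bias in the table, ln(0.883) = -0.12, lies inside both. That is fair on scale, but a systematic shift does not average out as the sample grows.

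A third reply is that the plan provides array analyses and, if an instrument is found, instrumental variable analyses. These are meant for what cannot be measured. Code 496 is in the claims and can be adjusted for directly.

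A reader might also infer more than the documents support:

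- That 496 carries most coded COPD. The documents give no split of claims between 491, 492, 493 and 496.
- That the problem is specific to benzodiazepines. The protocol does cite a "significant increase in mortality associated with adjunctive benzodiazepine use compared to antipsychotic monotherapy", but that comparison is with monotherapy, whereas the usual reference here is a second antipsychotic. Nothing in the documents says that COPD steers benzodiazepine prescribing. The omission affects all four strategies.
- That a harm is masked, or that it is exaggerated. The documents do not say which arm has more COPD.

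**Conclusion.** The omission is confirmed from the code list. COPD recorded only as 496 is balanced indirectly at best, and this can leave residual confounding of death and all-cause hospitalization in any treatment contrast. Both are secondary outcomes. The argument does not extend to the primary outcome, psychiatric hospitalization.

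The size rests wholly on assumed inputs. With 3-5% versus 5-10% and a relative risk of 2-3, the factor is 1.00 to about 0.88, or 1.00 to about 1.13 if reversed, before any proxy control. It is probably modest and may be negligible, and its direction is unknown. The case for acting is that a measured baseline covariate has been left out and costs almost nothing to add.

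**What to change.** Add ICD-9-CM 496 to Appendix 2, in one of two ways:

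- as its own row, leaving the 491.xx and 492.xx rows as they are; or
- in a combined COPD row (491.xx, 492.xx, 496) that replaces those two rows.

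Keep asthma (493.xx) separate in either case. Include the new row in the propensity model and report its standardized difference after weighting in each contrast. If 496 was left out on purpose, state the reason. Nothing in this point argues for adding further codes.

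The cost is a one-line edit and one more indicator drawn from the same diagnosis claims as the other rows. No sample size, power or alpha figure changes. In the smallest cell of Table 5 (611 episodes), an assumed prevalence of 3-10% would mean about 18 to 61 episodes (611 x 0.03 and 611 x 0.10). If a separate 496 row proves too sparse there, the combined row is the more stable choice.

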## Appendices:

### Appendix 1: Exclusion Diagnoses

### Appendix 2: Variables included in propensity scores

## Appendix 1: Exclusion Diagnoses (Contraindications for clozapine, other antipsychotics, or life threatening)

Diagnosis	ICD-9-CM Codes*
Narrow angle glaucoma	365.02
Myocarditis	422.x, 391.2x, 398.0x
Neutrophil disorders	288.00-288.04, 288.09, 288.1x
Malignant neoplasms	140-205
Epilepsy, seizure disorders	345.xx
Alzheimer's and other cerebral degenerations	331.xx

\* x indicates inclusion of any 5th digit if available for a diagnosis code.

xx indicates inclusion of any 4th and 5th digits if available for a diagnosis code.

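### The code range for the intracranial injury covariate takes in codes that the same table labels as fractures, hip fracture included, so the flag does not isolate head injury

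*Combined protocol and SAP*

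**What the plan says.** Appendix 2 of the combined protocol and SAP lists the propensity-score variables. Three rows of its past-year diagnosis table bear on this point:

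- "Intracranial injury 815.xx-854.xx"
- "Fractures, all sites 800.xx–829.xx"
- "Fracture of neck of femur 820.xx"

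The table's footnote says that the xx suffix takes in every fourth and fifth digit, so each range covers whole three-digit categories.

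Two other rows matter for a secondary query. One is "Hypertension 401.xx-405.xx". The other is the severe cardiovascular row, whose full code list is "401.0x-404.9x, 410.xx-416.xx, 425.xx-437.xx, 440.xx-447.xx".

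The section on the approach to confounding says that factors from the 365 days before drug initiation feed the propensity scores. The section on propensity score estimation and application enters all baseline predictors in a logistic model, adds a boosted-tree alternative, applies the scores by weighting, and judges balance by standardized differences after weighting.

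**The concern.** A covariate named for head injury should hold head-injury codes. This one starts inside the block that the same table gives to fractures and runs straight through hip fracture. No reading of the label makes that intentional, and a wrong lower bound is the natural explanation. The document has at least one other slip of this kind: the outcomes table starts its diabetes codes at 295, while Appendix 2 codes diabetes as 250.

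Adjustment is what is at stake. Intracranial injury has no other diagnosis row, so nothing else in the table makes good the loss if this flag is blurred. It is plausible, though the plan does not say so, that head injury affects both the choice of add-on drug and the outcome. The plan's mood-stabilizer class includes anticonvulsants, and its outcomes include admission, death and stroke. If so, a balance table showing a small standardized difference for intracranial injury would give more reassurance than it should.

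**Working it through.** The plan states no figure to reproduce. The check is an intersection of the printed code ranges, counted in three-digit categories, all from the Appendix 2 diagnosis table.

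**Intracranial injury**

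- Size of the range 815-854: 854 − 815 + 1 = 40 categories.
- Overlap with the all-sites fracture row (800-829): 815 to 829, so 829 − 815 + 1 = 15 categories.
- Share that the plan itself labels as fracture: 15/40 = 37.5%.
- Category 820, the femoral-neck fracture row, lies inside the overlap.
- Remainder: 40 − 15 = 25 categories (830-854). No other row of the table labels these, so the documents alone cannot say how many of them are head injury.

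**What balance on the flag means**

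Let a be the proportion of a treatment group with a true intracranial code, and b the proportion flagged only through some other code in the range. The flag's prevalence is a + b. Weighting that equalizes a + b across groups does not equalize a, because two groups can have the same total with different composition. A standardized difference near zero on this row therefore does not establish balance on head injury.

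**How large the dilution could be**

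Category counts do not measure patients, and the plan gives no code frequencies. As an illustration only, let f be the prevalence of the unwanted injury codes and i that of intracranial injury, and treat the two as independent. The share of flagged patients without intracranial injury is f(1 − i) / [f(1 − i) + i].

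- Assume f = 1%, i = 2%: 0.0098 / (0.0098 + 0.02) = 33%.
- Assume f = 8%, i = 0.5%: 0.0796 / (0.0796 + 0.005) = 94%.

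All four inputs are assumptions. The width of the result shows that the plan cannot settle the size.

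**Secondary query: severe cardiovascular row**

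- Size: 401-404 (4) + 410-416 (7) + 425-437 (13) + 440-447 (8) = 32 categories.
- Overlap with the hypertension row (401-405): 401-404, that is, 4 of the 5 hypertension categories (80%) and 4/32 = 12.5% of the severe row.
- Of the other 28, 17 fall in separately listed rows: 410-414 (5), 415-416 (2), 427-428 (2) and 430-437 (8). The remaining 11 (425, 426, 429, 440-447) appear in no other row.

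**The case against.** The strongest reply is that the fracture content is already handled. Both fracture rows enter the same model, so once the fracture flag is held fixed, the injury term should mainly reflect 830-854. This has some force, and it softens the problem without removing it. The all-sites fracture row also covers 800-814, which the injury flag does not. In a main-effects logistic model the injury coefficient is therefore still informed partly by the contrast of fractures at 815-829 with fractures at 800-814. A patient with both a fracture and a head injury cannot be told from one with a fracture in 815-829 alone. The reported balance for the row would still be balance on a mixture.

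A second reply is that the route to confounding is narrow. Appendix 1 excludes epilepsy and cerebral degenerations, past-year mood-stabilizer use is in the score, and the plan includes a sensitivity analysis for unmeasured confounding. All of that stands as a limit on the consequence. It gives no reason to leave a wrong code range in place.

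On the cardiovascular row the other side is stronger. The plan does not define severe, and a broad composite may be deliberate. Hypertension, ischemic heart disease ("Ischemic heart disease 410.xx-414.xx"), pulmonary circulation disease, dysrhythmia, heart failure and cerebrovascular disease each have their own row. Any redundancy in the composite does not take that adjustment away. This is why the row is raised only as a query.

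**Conclusion.** The point holds for the intracranial injury row. By the plan's own labels, 15 of its 40 categories are fractures, hip fracture among them, and the covariate has no substitute row. The flag therefore does not isolate the condition that it names, either in the propensity model or in the balance check. This conclusion needs nothing beyond the printed table.

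Three stronger readings are tempting, and the documents do not support them.

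- A reader might infer that most flagged patients have no head injury, or that the covariate has ceased to measure it. Either would require prevalences that the plan does not give, and the illustrative share runs from 33% to 94% depending on the assumptions. The range extends to 854, so the intended codes appear to be diluted, not lost.
- A reader might infer that the severe cardiovascular flag is in effect a hypertension flag. By category, 28 of its 32 entries are not hypertension, and the share by patients is again unknown.
- A reader might infer that the treatment comparisons are biased. This is one blurred flag among dozens of covariates, and nothing in the plan shows that any estimate would move materially.

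The error is thus clear and of unknown, possibly small, effect. It deserves correction because it sits in a list that directly drives the adjustment and costs almost nothing to repair.

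**What to change.** Correct the lower bound of the intracranial injury row so that the range holds only intracranial injury codes. The range 850.xx-854.xx appears to be intended. The plan does not state this, so the study team should verify it against the ICD-9-CM code set before changing the row. Then fit the propensity scores, by both the logistic and the boosted approach, and check balance on the corrected covariate.

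Separately, ask the sponsor to confirm that 401.0x-404.9x is meant to be in the severe cardiovascular row. If it is, one sentence calling the row a broad composite would suffice. If it is not, narrow the row.

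The cost is one edited code range and a short clarification. If scores have already been fitted, they must be re-run. No new data or design change is needed, and the eligible cohort stays the same.
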